### **3.3.7 General considerations for safety assessments**

Time windows will need defining for any presentations that summarize values by visit. (Note: this also applies to the PRO data, as well as safety analyses) The following conventions should also apply:

- The time windows should be exhaustive so that data recorded at any time point has the potential to be summarized. Inclusion within the time window should be based on the actual date and not the intended date of the visit.
- All unscheduled visit data should have the potential to be included in the summaries.
- The window for the visits following baseline will be constructed in such a way that the upper limit of the interval falls half way between the two visits (the lower limit of the first post-baseline visit will be Day 0). If an even number of days exists between two consecutive visits then the upper limit will be taken as the midpoint value minus 1 day.
- For summaries showing the maximum or minimum values, the maximum/minimum value recorded on treatment will be used (regardless of where it falls in an interval).
- Listings should display all values contributing to a time point for a patient.
- For visit based summaries:
  - If there is more than one value per patient within a time window then the closest value to the scheduled visit date should be summarized, or the earlier in the event the values are equidistant from the nominal visit date. The listings should highlight the value for that patient that went into the summary table, wherever feasible. Note: in summaries of extreme values all post baseline values collected are used including those collected at unscheduled visits regardless of whether or not the value is closest to the scheduled visit date.
  - To prevent very large tables or plots being produced that contain many cells with meaningless data, for each treatment group visit data should only be

summarized if the number of observations is greater than the minimum of 20 and  $> 1/3$  of patients dosed.

- For summaries at a patient level, all values should be included, regardless of whether they appear in a corresponding visit based summary, when deriving a patient level statistic such as a maximum.
- Baseline will be defined as the last non-missing measurement prior to dosing with study treatment. For the re-treatment period then baseline is similarly defined as the last non-missing measurement prior to the first dose on the re-treatment period. For laboratory data, any assessments made on day 1 will be considered pre-dose. Alternatively, if two visits are equally eligible to assess patient status at baseline (e.g., screening and baseline assessments both on the same date prior to first dose with no washout or other intervention in the screening period), the average can be taken as a baseline value. For non-numeric laboratory tests (i.e., some of the urinalysis parameters) where taking an average is not possible then the best value would be taken as baseline as this is the most conservative. In the scenario where there are two assessments on day 1, one with time recorded and the other without time recorded, the one with time recorded would be selected as baseline. Where safety data are summarized over time, study day will be calculated in relation to date of first study treatment.

Missing safety data will generally not be imputed. However, safety assessment values of the form of “ $< x$ ” (i.e., below the lower limit of quantification) or “ $> x$ ” (i.e., above the upper limit of quantification) will be imputed as “ $x$ ” in the calculation of summary statistics but displayed as “ $< x$ ” or “ $> x$ ” in the listings. Furthermore:-

- For missing diagnostic dates, if day and/or month are missing use 01 and/or Jan. If year is missing, put the complete date to missing.
- For missing start AE dates, the following will be applied
  1. Missing day- Impute the 1st of the month unless month is the same as month of the first dose of study drug then impute first dose date
  2. Missing day and month -Impute 1st January unless year is the same as first dose date then impute first dose date
  3. Completely missing-impute first dose date unless the end date suggests it could have started prior to this in which case impute the 1st January of the same year as the end date
- For missing end AE dates, the following will be applied:
  - Missing day - Impute the last day of the month unless month is the same as month of the last dose of study drug then impute last dose date.

- Missing day and month – impute 31st December unless year is the same as last dose date then impute last dose date.
1. If a patient is known to have died where only a partial death date is available then the date of death will be imputed as the latest of the last date known to be alive +1 from the database and the death date using the available information provided:-
    - a. For Missing day only – using the 1st of the month
    - b. For Missing day and month -using the 1st of January.

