4.1 Enrollment/screening period

All screening and enrollment procedures will be performed according to the assessment schedule in [Table 2](#) and [Table 3](#).

Written informed consent and any locally required privacy act document authorization must be obtained prior to performing any protocol-specific procedures, including screening/baseline evaluations. All patients will be required to provide consent to supply a sample of their tumor (archival or recently obtained biopsy) for entry into this study. This consent is included in the main patient informed consent form (ICF).

All screening/baseline procedures must be performed within 28 days before the first dose of treatment (Days -28 to -1). Screening/baseline evaluations may be performed over more than 1 visit. SoC procedures performed for other purposes prior to informed consent suitable for use as screening evaluations need not be repeated if the patient/legal representative consents to allow use of these procedures for screening purposes. Informed consents of study procedures and tumor sample acquisition may be obtained prior to the 28-day screening window in order to permit tumor sample acquisition; results of PD-L1 testing must be available prior to randomization.

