6.2 Recording of adverse events

6.2.1 Time period for collection of adverse events

AEs and SAEs will be collected from the time of signature of informed consent throughout the treatment period and including the follow-up period (up to 90 days after the last dose of IP or until initiation of another therapy). AEs and SAEs collected prior to randomization will be reported as pre-randomization AEs and SAEs.

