### **3.3 Safety**

Safety and tolerability will be assessed in terms of adverse events (AEs) (including serious adverse events [SAEs]), deaths, laboratory data, vital signs, electrocardiograms (ECGs) and exposure. These will be collected for all patients. Data from all cycles of treatment will be combined in the presentation of safety data. ‘On treatment’ will be defined as assessments between date of start dose and 90 days following discontinuation of IP (i.e., the last dose of MEDI4736 monotherapy, MEDI4736 + tremelimumab combination therapy, or SoC) regardless of re-treatment period. For AEs, on treatment (or treatment-emergent AEs) will be defined as any AEs that started after dosing or prior to dosing and which worsens following exposure to the treatment. If an AE is not worse than the baseline (pre-dose) severity, then it will not be classified as TEAE.

Safety analysis set will be used for reporting of safety data.

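### SAP 3.3.7 start-date rules 1 and 2 for AEs lack the end-date check in rule 3, so an AE that ended before first dose can be given a start after its end

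*SAP*

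**What the plan says.** SAP 3.3.7 lists three rules for AE start dates.

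- **Rule 1, day missing:** the 1st of the month, "unless month is the same as month of the first dose of study drug then impute first dose date".
- **Rule 2, day and month missing:** "Impute 1st January unless year is the same as first dose date then impute first dose date".
- **Rule 3, start completely missing:** the first-dose date, "unless the end date suggests it could have started prior to this in which case impute the 1st January" of the year of the end date.

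Only rule 3 consults the end date.

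Three other provisions bear on this:

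- Protocol 6.2.1 states that "AEs and SAEs will be collected from the time of signature of informed consent throughout the treatment period", and SAP 3.3.1 agrees. AEs that begin and end before any study drug can therefore be in the database.
- SAP 3.3 defines treatment-emergent as "any AEs that started after dosing or prior to dosing and which worsens following exposure to the treatment".
- SAP 3.3.1 puts AEs that occur before treatment in the listings and leaves them out of the AE summary tables. SAP 4.2.13.1 does the same for those that did not worsen, and mentions one separate summary for events before dosing.

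**The concern.** The three rules treat the same event inconsistently. Take an AE that ended on 10 March in a patient first dosed on 20 March. If the site recorded no start date at all, rule 3 looks at the end date and places the onset before treatment. If the site recorded March, rule 1 places the onset on 20 March, ten days after the event was over. The more informative record gets the worse answer.

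Two things are at stake. The first is an impossible record, with start after end, that feeds into AE duration. The second is the possible appearance of a resolved screening event in the treatment-emergent tables, in the event rates, and in the time-to-onset summaries, where it would count as an onset on the day of first dose. SAP 4.2.13.1 specifies all of these outputs.

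**Working it through.** The plan states no figure to reproduce, so the check applies the rules literally to worked records.

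**Inputs**

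- The three start-date rules of SAP 3.3.7, and its rule that an end date with a missing day becomes the last day of the month (the exception for the month of last dose does not apply here).
- Assumed first dose: 20 Nov 2016.
- Rule 3's exception is read as applying when the end date is before first dose.
- Duration = end − start + 1 day. This is an assumption; the SAP gives no formula for AE duration. Plain subtraction changes each figure by one day and leaves every sign below as it is.

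**Results**

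| Record | Start as written | Duration as written | Start with end-date check | Duration with check |
|---|---|---|---|---|
| A. Rule 1: start Nov 2016, end 15 Nov 2016 | 20 Nov 2016 | 15 − 20 + 1 = −4 | 1 Nov 2016 | 15 − 1 + 1 = 15 |
| B. Rule 2: start 2016, end 15 Nov 2016 | 20 Nov 2016 | 15 − 20 + 1 = −4 | 1 Jan 2016 | 320 |
| C. Rule 2: start 2016, end Oct 2016 (set to 31 Oct) | 20 Nov 2016 | −20 + 1 = −19 | 1 Jan 2016 | 305 |
| D. Rule 3: start missing, end 15 Nov 2016 | 1 Jan 2016 | 320 | 1 Jan 2016 | 320 |
| E. Rule 1, other month: start Oct 2016, end 15 Nov 2016 | 1 Oct 2016 | 46 | 1 Oct 2016 | 46 |

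Records A to C are inverted as written. D and E are not, and the check leaves them unchanged. The result does not depend on the dates chosen: when rule 1 or 2 returns the first-dose date and the recorded end is earlier, the imputed start is later than the end by construction.

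**Does another provision catch it?** SAP 3.3 and 4.2.13.1 exclude an AE that is no worse than its pre-dose severity. That test compares severities, not dates, and a record whose start has been moved to first dose has no earlier severity to compare with. On its true dates the event could not have worsened after dosing, because it was over.

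**How often is the calendar condition met?** Averaged over all first-dose days in 2016, about 52% of the days from −28 to −1 fall in the calendar month of first dose and about 96% in its year. These are shares of days, not of events. They show only that a matching month or year is not exotic. They say nothing about how many AEs have a partial start date and an end date before first dose.

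**The case against.** The strongest reply is that the event is already excluded. SAP 3.3.1 and 4.2.13.1 keep pre-treatment AEs out of the summary tables, and a recorded end before first dose shows that the AE was pre-treatment, whatever start was imputed. This has force: the SAP does not say that classification uses only the imputed start. But it also does not say that the end date overrides that start, so a programmer meets two rules that disagree. The inverted dates remain either way.

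A reader might infer that every such event is certain to be misclassified as treatment-emergent. The documents do not support that. SAP 3.3 requires onset after dosing and gives no rule for an AE that starts on the first-dose date. The on-treatment window opens on that date, which favours counting it. Against that, SAP 4.2.13.1 separates AEs that occur before the first infusion on Study Day 1, and the only same-day convention in SAP 3.3.7, for laboratory data, treats Day 1 values as pre-dose.

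A reader might also take the whole four-week screening period as exposed. Protocol 6.2.1 says that AEs collected before randomization are reported as pre-randomization events, and Protocol 3.3 requires study drug within 5 working days of randomization. If that category is assigned at collection, the exposed interval shrinks to roughly a week. Neither document says how it is assigned when the start date is partial.

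Other points stand. Protocol 9.4 provides for queries on missing or inconsistent data, so few partial dates should survive. Safety is descriptive (SAP 4.2.13), the rule is the same in all arms, and medians barely respond to one or two odd values.

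Imputing the first-dose date is a sound conservative choice when the end date is missing or falls on or after first dose. It is not conservative when the end date shows that the event was already over.

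**Conclusion.** The drafting gap is real and minor. For an AE with a recorded end before first dose and a start known only to the month or year of first dose, rules 1 and 2 always produce a start after the end. Whether the event also reaches the treatment-emergent, onset and duration summaries depends on two things that the SAP leaves open: whether an onset on the first-dose date counts as after dosing, and whether the imputed start takes precedence over the exclusion of pre-treatment AEs.

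The number of events is probably very small; the documents give no count. OS and the multiple testing procedure are untouched. The point is worth correcting because rule 3 already contains the remedy, not because it could change a safety conclusion.

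**What to change.** Add one clause to start-date rules 1 and 2 in SAP 3.3.7: if the recorded end date is before first dose, impute the 1st of the month (rule 1) or 1 January (rule 2) in place of the first-dose date. The clause should cover a complete end date and a partial one that is clearly earlier. The event then stays pre-treatment and its start cannot exceed its end. The first-dose imputation is kept wherever the end date is missing, ambiguous, or on or after first dose.

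For rule 2, 1 January may precede consent by months. That is crude, but it is the convention that rule 3 already uses, and it affects only events that do not belong in the on-treatment tables.

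A short statement of whether an AE that starts on the first-dose date is treatment-emergent would remove the remaining ambiguity. The cost is a sentence or two in the SAP and one condition in the derivation code, with no new data.

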#### **3.3.1 Adverse events (AEs)**

AEs and SAEs will be collected from the time of signature of informed consent throughout the treatment period and up to 90 days after the last dose of IP (MEDI4736 + tremelimumab, MEDI4736, or SoC) or until initiation of another therapy (excluding palliative radiation as anti-cancer therapy) regardless of whether the AE occurred during re-treatment with tremelimumab or not. Any AE occurring before treatment with IP will be included in the data listings but will not be included in the summary tables of AEs.

The Medical Dictionary for Regulatory Activities (MedDRA) dictionary will be used to code the AEs. AEs will be graded according to the National Cancer Institute Common Terminology Criteria for AEs (CTCAE Version 4.03 or higher).

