#### 4.2.13.1 Adverse Events

All AEs, both in terms of current Medical Dictionary for Regulatory Activities (MedDRA) preferred term and Common Toxicity Criteria for Adverse Events (CTCAE) grade, will be listed and summarized descriptively by count (n) and percentage (%). The current MedDRA dictionary will be used for coding. Any AE occurring before treatment with IP and which did not worsen during the course of the study will be included in the AE listings, but will not be included in the summary tables (unless otherwise stated). These will be referred to as 'pre-treatment'. However, any AE occurring before the administration of the first infusion on Study Day 1 that worsens after Study Day 1 will be regarded as treatment emergent and thus will be included in the summary tables. Note: If an AE is not worse than the baseline (pre-dose) severity then it will not be classified as TEAE.

AEs observed up until 90 days following discontinuation of IP or until the initiation of the first subsequent therapy (excluding palliative radiation as a subsequent therapy) following discontinuation of IP (whichever occurs first) regardless of whether the AE occurred during re-treatment with tremelimumab or not will be used for reporting of all of the AE summary tables. This will more accurately depict AEs attributable to IP only as opposed to presenting all AEs reported up to 90 days following discontinuation of IP. This is due to the fact that a number of AEs up to 90 days following discontinuation are likely to be attributable to subsequent therapy. However, to assess the longer term toxicity profile, a small selection of the AE summaries may be repeated containing AEs observed up until 90 days following discontinuation of IP (i.e. without taking subsequent therapy into account). A summary will also be produced containing all AEs (by system organ class and preferred term) observed from the initiation of the first subsequent therapy following discontinuation of IP until 90 days following discontinuation of IP treatment (i.e. summarizing those AEs experienced by patients taking subsequent therapy during the 90 days AE collection follow-up window post discontinuation of IP). Any data post 90 days last dose will be listed only apart from a separate summary that presents any events that occur prior to dosing or starting more than 90 days after discontinuing IP.

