#### **Summary of long-term tolerability:**

To assess long term tolerability, provided that there are a sufficient number of patients with events to warrant it, prevalence plots, life table plots and cumulative incidence plots will be presented for each of the AESI grouped terms and any other events considered important after review of the safety data, provided there are  $\geq 10$  events, that is 10 events in at least one treatment group.

A prevalence plot provides information on the extent to which the events may be an ongoing burden to patients. The prevalence at time  $t$  after first dose of study treatment is calculated as the number of patients experiencing the event divided by the number of patients receiving study treatment or in safety follow-up at time  $t$ ; generally,  $t$  is categorized by each day after dosing. The prevalence will be plotted over time presented. Multiple occurrences of the same event are considered for each patient but a patient is only counted in the numerator whilst they are experiencing one of the occurrences of the event. These plots will only be produced for AESIs that have  $\geq 10$  events, that is 10 events in at least one treatment group.

For each AESI, median time to first onset of the AESI from the date of first dose will be presented in patients in the safety analysis. Patients who did not experience the AESI will be censored at the end of their safety follow-up. Summary tables of time to first onset for each AE will also be produced (e.g. 1-28 days, 29-56 days, 57-84 days, 85-112 days, >112 days). Median duration of the AE and AESI will be presented in patients who experienced each, as well as the median time to resolution to grade 1 or less and time to resolution to grade 2 or less.

A life table plot can be used to describe the time to onset of the event and specifically when patients are at most risk of first experiencing the event. The hazard, or in other words, the probability of having an AE in a specified time period (e.g. 0-1 months, 1-3 months, 3-6

months, etc.) given that the patient reaches that time period without having an event is plotted for each time period. These plots will only be produced for AESIs that have  $\geq 10$  events, that is 10 events in at least one treatment group.

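### The AE end-date imputation in SAP 3.3.7 has no floor at the AE start date, so some events that begin after the last dose are given an end date before their start

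*SAP*

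**What the plan says.** SAP 3.3.7 gives two rules for incomplete AE end dates.

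- **Day missing:** the end of the recorded month, "unless month is the same as month of the last dose of study drug then impute last dose date".
- **Day and month missing:** "impute 31st December unless year is the same as last dose date then impute last dose date".

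The start-date rule mirrors this at the other end of treatment: the first of the month, "unless month is the same as month of the first dose of study drug then impute first dose date". The end-date rule has no check against the AE start.

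AEs are gathered well past the last dose. SAP 3.3.1 collects them "throughout the treatment period and up to 90 days after the last dose of IP", and Protocol 6.2.1 agrees: "up to 90 days after the last dose of IP or until initiation of another therapy". SAP 4.2.13.1 bases the summary tables on "AEs observed up until 90 days following discontinuation of IP or until the initiation of the first subsequent therapy".

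Under the long-term tolerability heading, the SAP plans two outputs that need end dates: "Median duration of the AE and AESI will be presented in patients who experienced each", and prevalence plots in which "a patient is only counted in the numerator whilst they are experiencing one of the occurrences of the event".

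**The concern.** The date of the last infusion says nothing about when an AE resolved. For an event that began after that infusion it cannot be the end date at all. This group is not exotic. MEDI4736 is given every four weeks (Protocol 7.2.1), so an event that arises between infusions and ends treatment necessarily starts after the last dose.

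The same section of the SAP applies the missing safeguard elsewhere. A partial death date cannot be imputed earlier than the day after the patient was last known alive, and the rule for a completely missing AE start date looks at the end date. The end-date rule alone has no such check.

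At stake are the descriptive duration outputs. A negative duration pulls the median down. In a prevalence plot, an interval that ends before it begins contributes no time with the event, although the event occurred. Without a written rule, the programmer must either report impossible values or devise a correction after seeing them.

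**Working it through.** The plan states no figure to reproduce, so the check applies the rule as written. I read the same month as the same calendar month and year, which the SAP does not spell out. Duration is counted as end − start + 1, also an assumption.

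**Step 1: general result.** Let L be the last dose date, S the AE start and E the imputed end. When the exception is met, E = L. If S > L, then E − S = L − S < 0, without exception.

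- Day missing: start and end both lie in the month of L, so the gap is 1 to 30 days.
- Day and month missing: S can be up to 90 days after L, so the gap is 1 to 90 days.

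**Step 2: worked dates** (the year 2018 and the true end dates are illustrative).

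| Case | Last dose | AE start | True end | Recorded end | Imputed end | Imputed duration | True duration |
|---|---|---|---|---|---|---|---|
| A | 10 Mar | 20 Mar | not set | March | 10 Mar | −9 | – |
| B | 5 Mar | 12 Mar | 25 Mar | March | 5 Mar | −6 | 14 |
| C | 5 Mar | 10 May | 20 May | 2018 | 5 Mar | −65 | 11 |
| D | 5 Mar | 1 Mar | 25 Mar | March | 5 Mar | 5 | 25 |
| E | 5 Mar | 1 Feb | 20 Jun | 2018 | 5 Mar | 33 | 140 |
| F | 25 Mar | 1 Mar | 10 Mar | March | 25 Mar | 25 | 10 |

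Cases A to C start after the last dose and are impossible. D and E continued past the last dose and are cut off at it. F ended before the last dose and is lengthened.

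**Step 3: how often the exception is met for onsets after the last dose.** I enumerated every last-dose day of a non-leap year with onset 1 to 90 days later (365 × 90 = 32,850 combinations), for three assumed true durations.

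| True duration | Day missing | Day and month missing |
|---|---|---|
| 7 days | 10.5% | 85.9% |
| 14 days | 5.2% | 84.0% |
| 28 days | 0.2% | 80.1% |

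These percentages are conditional on the end date being partial in that way. In every combination that met the exception, the imputed end preceded the start.

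**Step 4: direction of error in general.** Take a true end day uniform over the month of the last dose, regardless of when the event started. The imputed date is too early in 48.4% of combinations, too late in 48.4% and exact in 3.3%.

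**The case against.** The strongest reply is that the last dose date is a reasonable central guess. If the last-dose day and the true end day are independent and uniform over a 31-day month, imputing the last dose has mean error 0 and mean absolute error (31² − 1)/(3 × 31) = 10.3 days. Imputing the end of the month has mean error 31 − 16 = +15 days and mean absolute error 15. That stands for events that could have ended on either side of the last dose. It does not cover events that started after it or are known to have outlasted it, because for those the true end lies on one side only.

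This argument also disposes of a stronger reading that a reader might draw: that the rule shortens AE durations generally, by up to 30 days or up to a year. That is true only against the SAP's own end-of-month and 31 December defaults. Against true end dates, about as many events are lengthened as shortened.

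The second reply is that the reach is small. Start and stop dates are required AE variables (Protocol 6.2.3), and missing or impossible data are queried (Protocol 9.4). The exception also needs a partial date in the right month or year. This stands, and it keeps the point minor. Queries reduce the number of partial dates but do not repair an imputed one.

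Third, not every duration-type output need be affected. Changes in toxicity grade are collected separately (Protocol 6.2.3), so time to resolution to grade 1 or 2 may not use the AE end date. This stands too. The SAP does not say which date it uses.

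**Conclusion.** The rule is wrong as written for a defined group. Any event that starts after the last dose and meets the exception is given an impossible end date, up to 30 days before its start when the day is missing and up to 90 when the month is missing as well. An event known to be ongoing after the last dose is truncated there. The result rests on the rule's wording and the 90-day window. Only the trigger frequencies depend on assumed durations.

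The effect is confined to descriptive safety outputs: median duration of AEs and AEs of special interest, prevalence plots, and possibly time to resolution. AE incidence counts and overall survival do not use AE end dates. The number of partial end dates is unknown, so the effect on any reported median cannot be sized.

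A reader might also infer a bias between arms, because cetuximab is given weekly and MEDI4736 every four weeks. The documents give no count of partial dates by arm, so they support neither a direction nor a size. This is a minor point, worth correcting because the correction is easy.

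**What to change.** Add to SAP 3.3.7:

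1. An imputed AE end date is never earlier than the AE start date.
2. The last-dose exception does not apply to an event that starts after the last dose, or that another record (such as a later grade change) shows to be ongoing after it. For these, use the SAP's own default, the end of the recorded month or 31 December, limited by death or data cut-off and kept within the recorded month or year.
3. The same month means the same calendar month and year.

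Under this rule, case A ends on 31 March (31 − 20 + 1 = 12 days) and case B on 31 March (20 days). Case F is unchanged.

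A cap at the end of the 90-day follow-up is better avoided. Protocol 6.2.2 has AEs pursued to resolution even after treatment stops, so a recorded end month can fall later than day 90, and the cap would then contradict the site's record.

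The cost is a sentence or two and a small programming change, with no new data. One drawback should be accepted openly: with the month missing, 31 December can overstate duration considerably. Case C becomes 236 days against a true 11, unless death or data cut-off comes first. A footnote giving the number of imputed end dates per arm would let readers judge this.
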